the device based on a lack of development of significant closed set (more than pattern perception) or open set speech perception, and failure to achieve developmentally appropriate language growth during the follow up period. Those without a present or patent cochlea will be implanted with the ABI without the need for previous CI. Post-linguistic children (<18 yrs) will have had a CI but lost or lacked benefit from an appropriate CI and have no potential for revision CI surgery to improve their condition. The side/ear contralateral to the previous placed CI will be chosen, unless not possible (eg. bilateral CIs), to avoid potentially same-side, unwanted surgical and processor interactions as well as to allow comparison of performance in the follow-up period. If ABI needs to be considered ipsilateral to the previous CI, removal of the CI will need to be considered. Surgical interaction would be the issue of needing to operate in and around the CI device putting it at risk of damage. Unwanted processor interactions would be problematic if the receiver stimulator of the previous CI and the ABI were located in the same region. The ABI processor headpiece might be attracted to the CI receiver stimulator.

Following implantation of the investigational device and at least 4-6 weeks of healing, the ABI will be activated in a controlled setting and auditory performance assessed at the previously proposed intervals (1, 3, 6, 12, 18, 24, 30, 36 months). Subjects will be evaluated using the Nucleus Speech Processor and programmed with an approved sound processing strategy. Post-operative auditory function will be evaluated using behavioral audiometry and commonly used, developmentally appropriate measures of speech perception, speech production and language. Auditory function will also be assessed using electrophysiological tests at appropriate intervals.

SPECIFIC AIMS

Aim 1: Demonstrate the safety of ABI surgery in children.

Aim 2: Demonstrate the development of sound awareness and improved speech understanding among children implanted with the ABI when compared to their baseline skills.

Aim 3: Demonstrate the development of oral language skills following the use of the ABI that were not evident prior to its use.

Methods and Subjects

Up to 10 subjects will be enrolled in the study at the sponsoring location. Qualified subjects must meet the following inclusion criteria and must not exhibit any of the exclusion criteria.

Inclusion Criteria

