- Pre-linguistic hearing loss (birth-5 yrs.; age at ABI 18 months-5yrs) with both:
 - MRI +/- CT evidence of one of the following:
 - Cochlear nerve deficiency
 - Cochlear aplasia or severe hypoplasia
 - Severe inner ear malformation
 - Post-meningitis ossification
 - When a cochlea is present or patent, lack of significant benefit from CI despite consistent use (≥ 6 mo.)
 - No or limited speech perception ability (limited to pattern perception on closed set testing materials using the CI)

- Lack of progress in auditory skills development

18 months of age was chosen for the lower age limit to minimize the adverse effects of auditory deprivation on speech perception, speech production, and language development (23, 50). Moreover, 18 months of age will allow for a child to receive a CI at 1 year of age and have at least 6 months of device experience prior to considering ABI. Six months of CI usage prior to ABI consideration was chosen as this time period to allow for clear demonstration of lack of benefit as defined as either: (1) lack of sound awareness, or (2) where elevated charge requirements, absent ECAPs, elevated pure tone averages (>45 dB), and no or limited speech perception abilities are evident. To determine if a child is making significant progress both subjective and objective measures are used. Objectively, standardized speech perception, production, and language tests (as described below) are administered to determine if standard scores are following typical developmental patterns, even at a reduced rate. No or limited speech perception abilities will be considered when there are no improvement in IT-MAIS, or ESP measures from preop measures at the 6 month post-CI interval (30, 50). Developmental norms are also determined based on the hearing age. For example, a child who is 9 months old receptively understands between 3 and 50 vocabulary words and approximately 300 between the ages of 2 and 3. Does the child with a hearing age of 9 months understand this many words? For early speech development, all English vowels should be present by a hearing age of 12 months. Children 18 months of age can be tested using the standardized measures to determine progress.

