A single-subject research design was chosen (in which each subject serves as their own control) in order to accommodate for the heterogeneity that is well known to characterize auditory prosthesis research. Post-operative evaluations will be conducted at the initial activation and at 1, 3, 6, 12, 18, 24, 30, and 36-month intervals post-activation. Blinding or masking procedures are not included in the design, as the presence/absence of a brainstem implant cannot be easily concealed from the device recipients and/or clinical investigators.

Data will include demographics, frequency of both major and minor complications as well as audiometric and speech and language data. The summary statistics will be reported on the various categorical (gender and complications) and continuous (age, audiological and speech perception, production and language scores) variables.

Baseline audiological and speech perception, production and language measures taken prior to ABI surgery will be compared to scores at each follow up interval within each subject. For subjects with no response on behavioral testing, a maximum score of 120 dB HL will be assigned at the test frequency as this represents maximum stimulus levels of the equipment. Pure tone average (PTA) is calculated using the thresholds from 500, 1,000, and 2,000 Hz. When speech perception testing is limited by short duration experience or young age, inattention, or the presence of significant comorbidities, these reasons will be recorded. When inability to complete the test is evident despite significant implant experience, the patient is assigned the value for chance correct responses for the appropriate test (i.e., 0% for open-set tests or 33% for ESP pattern-[P] perception tests). When a child advances out of a particular measure because of ceiling effects, then the next measure will be undertaken. For children able to perform a given speech perception measure(s) prior to ABI surgery, that measure(s) will be repeated at the initial post-operative visits to insure the same test comparisons exist. It will be assumed that children that are unable to perform closed set testing will not be able to perform open set testing at a given visit. Thus, scores on these tests will be assigned the value of “unable to test”.

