Change values for each of the variables will be calculated by subtracting off baseline values when available. The mean percent change at the various intervals for each variable can be averaged (+/- SD) across the subjects. Comparison to baseline measures for significance testing will be made with 95% confidence intervals when possible. The chance that this is not possible exists because of the broad variation in ages and possible achievements with the device.

For speech perception, there is a developmental hierarchy that is required to evaluate the emergence of this skill over time. This will be tracked and plotted on a graph against similar children with normal hearing as well as those fitted with CIs with and without malformations for comparison (30, 50). This modified cumulative speech perception index in quiet (SRI-Q) will be created after Wang et al. (50) and Buchman et al (30) in an effort to simultaneously display the data from all tests in the speech recognition hierarchy as a function of time. ESP-P is considered easier than ESP-monosyllabic (M) words. CNC word scores then follow PB-k word scores. The measured percentage score for each test (0%–100% correct) is then hierarchically ranked and stacked in 100-point increments. These results are controlled for duration of device usage and age at implantation. Speech production and language data are reported as age-normed values and will be compared to children of a similar age with normal hearing as well as those using CIs.

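### Change is defined by subtraction but averaged as a percent change for each variable, which is undefined from a 0% open-set baseline and arbitrary for dB HL thresholds

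*Combined protocol and SAP*

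**What the plan says.** All of the analysis text is in Data and Analysis. Change is first defined as a difference: "Change values for each of the variables will be calculated by subtracting off baseline values when available". The next sentence uses another scale: "The mean percent change at the various intervals for each variable" is what may be averaged, with its SD, over the children. No formula is given, no rule covers a zero baseline, and no outcome is exempted. The continuous variables listed in the section include age and the audiological, speech perception, production and language scores.

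The same section sets the values that can serve as baselines:

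- No response at a test frequency is recorded as 120 dB HL.
- "When inability to complete the test is evident despite significant implant experience", the child receives the chance score: "0% for open-set tests or 33% for ESP pattern-[P] perception tests".
- Where short experience, young age, inattention or comorbidity limits speech perception testing, the reason is recorded; no score is mentioned.
- The plan assumes that "children that are unable to perform closed set testing will not be able to perform open set testing at a given visit", and codes those tests as untestable rather than 0%.

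Eligibility determines who has which baseline. Under Inclusion Criteria, pre-linguistic children with a present or patent cochlea must have no speech perception, or perception "limited to pattern perception on closed set testing materials using the CI". Under Protocol, "Those without a present or patent cochlea will be implanted with the ABI without the need for previous CI".

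**The concern.** A percent change divides by the baseline. That needs a baseline above zero and a scale whose zero means none of the quantity. Two of the trial's main outcome types fail this requirement.

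Open-set speech scores can start at 0% by the plan's own assignment rule. Emergence of open-set perception is the reason given for three years of follow-up (Protocol; Study Endpoints). A child who goes from 0% to a measurable open-set score therefore has no value to contribute to this mean.

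Thresholds in dB HL are on a logarithmic scale with a conventional zero. The percentage then depends on where the child started and where the scale's zero was put, as well as on the gain.

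What is at stake is the group mean and SD for these outcomes, and any 95% confidence interval computed on that scale.

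**Working it through.** The plan states no percent-change figure, so there is none to reproduce. The formula used is the ordinary one:

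percent change = 100 × (follow-up − baseline) / baseline, set against absolute change = follow-up − baseline.

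Three baselines come from Data and Analysis: 0% (open-set), 33% (ESP pattern perception) and 120 dB HL (no response). All other baselines, and all follow-up values, are assumed for illustration.

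**1. Zero open-set baseline.** For 0% to 20%, 100 × (20 − 0)/0 is undefined. For 0% to 50% it is undefined again. The absolute changes are +20 and +50 points.

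**2. Low non-zero baselines.** Give five children the same 20-point gain:

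| Baseline | Follow-up | Absolute change | Percent change |
|---|---|---|---|
| 2% | 22% | +20 | +1000% |
| 4% | 24% | +20 | +500% |
| 10% | 30% | +20 | +200% |
| 20% | 40% | +20 | +100% |
| 30% | 50% | +20 | +67% |

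The mean percent change is (1000 + 500 + 200 + 100 + 66.7)/5 = 373%, with SD 390%. The absolute gains have mean 20 and SD 0. All the spread on the percent scale comes from the baselines.

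**3. Assigned ESP pattern baseline.** 33% to 66% gives 100 × 33/33 = +100%. 33% to 100% gives 100 × 67/33 = +203%, against +67 points. The percentage is scaled by an assigned chance value.

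**4. Thresholds.** The same 40 dB gain from three starting points:

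- 120 to 80 dB HL: −40/120 = −33.3%
- 90 to 50 dB HL: −40/90 = −44.4%
- 60 to 20 dB HL: −40/60 = −66.7%

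The result also depends on the reference level. A gain from 120 to 40 dB HL is −80/120 = −66.7%. Moving the zero so that every value rises by 10 dB gives −80/130 = −61.5%; lowering every value by 10 dB gives −80/110 = −72.7%. The difference stays at −80 dB throughout.

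**5. Baselines that are not numbers.** If the baseline is missing or coded untestable, neither formula gives a value. Changing to absolute differences repairs items 1 to 4 but not this one.

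**6. The coding rules side by side.** Take a child with significant implant experience who cannot do closed-set testing. The chance-score rule gives 0% on the open-set tests; the closed-set rule gives the untestable code. The first allows an absolute change and the second does not, and the section does not say which takes precedence.

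**The case against.** The best defence is that percent change is loose wording for percentage points. The preceding sentence defines change by subtraction, speech scores are already percentages, and a point difference is defined at 0%. This is plausible for the word and sentence tests. It cannot serve for dB thresholds or for the age-normed production and language values, yet the sentence covers every variable. The text is therefore at least ambiguous, and the two readings give very different results.

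The second defence is that little depends on the summary, and this largely stands. The averaging is worded as an option. The design compares each child with his or her own baseline. The SRI-Q stacks raw percentage scores and needs no ratio to baseline. Study Endpoints looks at whether open-set perception appears by three years. A child who gains open-set speech is not lost from the evaluation, only from this mean.

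A reader might infer three stronger things that the documents do not support:

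- *Every pre-linguistic child has a 0% open-set baseline.* The 0% rule requires significant implant experience, the pattern-perception limit applies when a cochlea is present or patent, children without one may have had no CI, and others will be coded untestable.
- *All five open-set tests fail by division by zero.* The battery in Audiological Assessment is gated: LNT follows MLNT above 50%, and CNC follows LNT above 80%. Many higher tests would simply not be given at baseline.
- *The remaining mean would rest mainly on post-linguistic children.* Inclusion Criteria requires them to have lost, or lacked, benefit from the CI. Only past open-set ability is required, so their current baseline may also be 0%.

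**Conclusion.** The point holds in a limited form. Read as change relative to baseline, the planned summary is undefined for any child with a 0% open-set baseline, unstable for low baselines, and arbitrary for dB HL, where equal 40 dB gains range from −33% to −67% in the illustration. Read as percentage points, it does not fit all the variables it is said to cover. Neither reading works across the outcome set.

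The number of children affected cannot be derived from the documents, because it depends on how many baselines are 0%, untestable or missing. The arithmetic rests on the plan's assigned baselines and on assumed follow-up values; it shows how the measure behaves and does not predict the trial's results. The within-subject comparisons and the SRI-Q display are unaffected. This should be corrected before analysis, but it does not threaten the main evaluation.

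**What to change.** In Data and Analysis:

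1. Delete the word percent from the averaging sentence. Report mean absolute change with SD and, where feasible, a 95% confidence interval on each measure's own scale: percentage points for speech perception scores, dB for thresholds and PTA, and raw or standard-score points for questionnaires and language tests.
2. State the number of children contributing to each mean at each visit.
3. For children whose baseline is untestable or missing, report separately at each visit the count who attain a measurable score.
4. Reconcile the chance-score rule with the untestable rule, so that a given child at a given visit can receive only one code on an open-set test.

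The cost is a few sentences of text. No test, visit or sample size changes, and no new data are collected.

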It is anticipated that this pilot study will be used to demonstrate safety and give some idea regarding efficacy. However, a larger scale clinical trial will be needed beyond the pilot study to demonstrate surgical safety on a broader scale (across surgeons and institutions) and the utility of the device for the intended auditory benefits. Ten subjects should be a sufficient sample size to demonstrate safety. If the European data is correct regarding complication rates in children, a single CSF leak might occur in one subject and non-auditory side effects can be expected to occur in roughly 20% of children or 2 subjects in this study. This number seems to be a conservative and reasonably small number to demonstrate these effects. Non-auditory stimulation is not serious and can be programmed around with simple changes in device programming during activation. For speech perception and production, the within subject design should allow us to see some benefit from the device if effective. Since the children are deaf, any development of significant open or closed set perception (beyond patten perception) would be attributable to the device. Similarly for language outcomes although these will take longer time to develop. Thus, the safety numbers are the drivers in powering this study.

The data will be recorded in patient-specific binders on a case-by-case basis after each subject encounter. All data will be entered in to the secure, File Maker Pro, customized database for CI research housed in the Department of Otolaryngology-Head and Neck Surgery that is currently in use. The lead investigator will cross check the data prior to approval for review. The data will be exported by desired fields to an Excel spreadsheet (Microsoft) for further analysis. Statistics will be carried out using SPSS software. If needed, statistical consultation will be sought at the University TRACS or Odum Institute.

Study Endpoints

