Study endpoints are based on the 3 specific aims. For safety, this will be determined on a case-by-case basis and any adverse events will be reviewed with the IRB and the data monitoring board (2 individuals appointed). Should the adverse events be deemed unacceptable to the investigators, the IRB, or the monitoring board, this would be sufficient terms for study discontinuation. Three years of follow up was chosen to provide adequate time for the emergence of open-set speech perception abilities in the pre-lingual cohort of children. In studies of prelinguistic children undergoing CI, at least 2 years of follow-up is needed to demonstrate emergence of these skills (23). If no open set perception is demonstrated at 3 years, this seems to be good evidence for a lack of benefit on this measure. In general, speech and language measures should track speech perception abilities. While the full emergence of these skills can take

somewhat longer to develop, it is anticipated that early emergence will be evident if speech perception is developing. While not anticipated, a clear lack of benefit from the device (such as no sound awareness) among multiple subjects would also be consideration for stopping the study. Study recruitment is expected to be slow at 1-3/year. This will not stop the study.

Human subject protection measures

Risks and measures to minimize risk. There is limited psychological, social, legal and economical risk to patients for participating in this study. The potential for a confidentiality breach is rare. All children and their parents will be treated confidentially according to HIPAA and its requirements. All discussion of the results of the intervention for the purposes of results reporting will be made anonymously.

The physical risks include medication side effects, pain, discomfort, or injury from participation. The potential risks from participation are likely (10-25%) and dependent on the consequences in question. The potential complications have been detailed above.

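### Ten subjects cannot demonstrate surgical safety: the plan sets no rate or precision target, and zero events in ten leave a 95% upper limit of 30.8%

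*Combined protocol and SAP*

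**What the plan says.** In Specific Aims, the first aim reads "Aim 1: Demonstrate the safety of ABI surgery in children". The sample-size paragraph in Data and Analysis says "Ten subjects should be a sufficient sample size to demonstrate safety". It supports this with two forecasts attributed to European data in children: possibly one CSF leak, and non-auditory side effects in about 20%, or two children. It adds "This number seems to be a conservative and reasonably small number to demonstrate these effects", and says of the second forecast: "Non-auditory stimulation is not serious and can be programmed around with simple changes in device programming during activation". After a remark on efficacy it closes with "Thus, the safety numbers are the drivers in powering this study".

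On analysis, the same section says "The summary statistics will be reported on the various categorical (gender and complications", in a list that continues with the continuous variables. The one interval it mentions is tied to change from baseline: "Comparison to baseline measures for significance testing will be made with 95% confidence intervals when possible". Study Endpoints says "For safety, this will be determined on a case-by-case basis", with review by the IRB and a two-person monitoring board. The study may be stopped if events are judged unacceptable, but no numerical threshold is given.

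The number of children is not stated consistently. The Protocol section, Methods and Subjects, and the sample-size paragraph all work with ten in total. The opening purpose paragraph proposes up to ten pre-linguistic children and five post-linguistic children.

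**The concern.** A sample size justified by safety needs a rate to be excluded, a precision to be reached, or a stated chance of detecting an event of interest. The paragraph gives expected counts, which are forecasts and not criteria. A surgical complication has no baseline value, so the planned 95% intervals do not reach it. The only event that ten children can be relied on to show is the one the paragraph plays down, while Aim 1 is about the operation.

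The practical risk is that a clean complication table in ten children is read as surgical safety having been shown, and that the larger trial is planned on that footing.

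**Working it through.** **Inputs**
- N = 10 (sample-size paragraph, Protocol, Methods and Subjects); 15 if the opening paragraph's ten plus five applies.
- 20% for non-auditory effects (sample-size paragraph).
- 29 children without tumour in the European complications series (Complications from Auditory Brainstem Implantation). Table 2 lists one cerebellar contusion and one meningitis among them, so 1/29 = 3.4% for each.
- Below 1% for cerebellar injury and below 2% for meningitis, from the adjacent surgical literature quoted in Potential Risks.

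**The plan's own figures.** 20% × 10 = 2, as stated. The individual effects listed for children (2 + 2 + 1 + 1 + 1) sum to the 7 in Table 2, and the quoted 6.9% and 3.4% equal 2/29 and 1/29, which confirms the denominator. If each effect is one child, 7/29 = 24.1%, which is compatible with roughly 20%. N = 10 itself cannot be reproduced, because no alpha, power, acceptable rate or interval width is given.

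**What ten can exclude.** For x events in n, the two-sided exact (Clopper-Pearson) 95% limits are the 0.025 quantile of Beta(x, n − x + 1) and the 0.975 quantile of Beta(x + 1, n − x). With x = 0 the upper limit reduces to 1 − 0.025^(1/n).
- 0/10: 1 − 0.025^(1/10) = 0.308, so 30.8%. The one-sided 95% limit is 1 − 0.05^(1/10) = 25.9%.
- 0/15: 1 − 0.025^(1/15) = 0.218, so 21.8%.
- 1/10: 0.25% to 44.5%.
- 2/10: 2.5% to 55.6%.

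The last two are the outcomes that the paragraph itself forecasts.

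**What ten can reveal.** P(at least one event) = 1 − (1 − p)^n.

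| True rate p | n = 10 | n = 15 |
|---|---|---|
| 20% | 1 − 0.8^10 = 89.3% | 96.5% |
| 10% | 1 − 0.9^10 = 65.1% | 79.4% |
| 1/29 | 1 − (28/29)^10 = 29.6% | 40.9% |
| 2% | 1 − 0.98^10 = 18.3% | 26.1% |
| 1% | 1 − 0.99^10 = 9.6% | 14.0% |

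A complication with a true rate of 10% would therefore be absent from all ten children 34.9% of the time. An 80% chance of seeing at least one event requires a true rate of at least 1 − 0.2^(1/10) = 14.9% with ten children.

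**The case against.** The strongest reply is that this is an early feasibility study. The opening paragraph speaks of an attempt to show safety and of preliminary experience. The sample-size paragraph itself says that a larger trial must establish surgical safety over more surgeons and centres. Safety is handled by individual review with external oversight, and in such a design the lack of a formal threshold is not in itself a fault. The narrower statement that ten is enough to show the forecast effects fits the 89% figure. The paragraph also names a surgical event, the CSF leak, and not only stimulation effects. Finally, any reader given n and N can compute an exact interval.

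Most of this stands, and it is why no larger study is called for. It does not rescue the sentence. Deferring safety on a wider scale still implies that safety at this centre will have been shown, and the next sentence says ten suffices for that. The leak does not change the picture: even at one in ten, the chance of seeing any leak is 65%.

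A reader might go further and infer that the leak forecast has no source. The documents do not support that. The paragraph names European data in children, the complications section cites a leak in a child, and part of the background text was not available here, so a missing denominator cannot be claimed. A reader might also infer an arithmetic error, but the plan's one calculation reproduces.

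**Conclusion.** The point holds as a defect in the sample-size justification. The plan claims a property that ten children cannot deliver for Aim 1. Zero events leave rates up to 30.8% compatible with the data, and serious surgical events at the rates the protocol quotes would more often than not go unseen: about a 30% chance of observing one at 1/29, and under 19% below 2%. With fifteen children the figures are better (21.8% upper limit, 41% at 1/29), but the conclusion is the same.

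The figures rest on independent children with a common risk, on two-sided exact limits, and on one event per child for the Table 2 counts. The 1/29 rate is a rough guide from a single event. The text also places the child with the contusion at a centre other than the one where the series is said to have been performed.

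It would be too strong to infer that the study is too small for its purpose or that N must rise. The documents set no rate against which ten could be judged inadequate, and ten is enough to show frequent stimulation effects.

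The text's single major complication in a child, against two child events listed as major in Table 2, is a separate minor note that does not bear on the sample size; the two events could be in one child.

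**What to change.** 1. In the sample-size paragraph of Data and Analysis, replace the sentence on sufficiency with wording such as: *The study will give preliminary estimates of complication frequencies; with 0 events of a given type in 10 subjects the two-sided exact 95% upper limit is 30.8% (21.8% in 15). Ten subjects give an 89% chance of observing at least one event occurring at 20%, about 30% at 1/29, and under 19% for events below 2%.*
2. In the paragraph on summary statistics, report each complication as n/N, with n the number of children affected, and a two-sided Clopper-Pearson 95% interval.
3. Reconcile the total N across the opening paragraph, Protocol, Methods and Subjects, and the sample-size paragraph, and quote the matching figures. For fifteen these are 21.8%, 96%, 41% and under 27%.

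The cost is a few text edits and one interval per complication, with no added subjects or visits. The downside is that the stated safety claim becomes more modest.
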